4.3. Withdrawal Criteria and Procedures for the Patient

Each patient is free to withdraw from the study or discontinue from IMP or using the devices at any time, without prejudice to their continued care. Patient must be withdrawn from the study if any of the following events occur:

- 1. Patient withdraws consent or requests discontinuation from the IMP or withdrawal from the study for any reason.
- 2. Patient develops an illness that would interfere with his/her continued participation.
- 3. Patient is noncompliant with the study procedures and assessments or administration of FS eMDPI or Albuterol eMDPI, in the opinion of the investigator.
- 4. Patient takes prohibited concomitant medications as defined in this protocol (ie, other SABA products).
- 5. The sponsor requests withdrawal of the patient.
- 6. Patient experiences an adverse event or other medical condition which indicates to the investigator that continued participation is not in the best interest of the patient.

Patients should be treated with SoC after withdrawal from or termination of the study as appropriate.

Investigators should attempt to obtain information on patients in the case of withdrawal from the study or discontinuation from IMP. Results of any evaluations and observations, together with a narrative describing the reason(s) for withdrawal from the study or discontinuation from IMP, must be recorded in the source documents. The case report form (CRF) must document the primary reason for withdrawal from the study or discontinuation from IMP.

See Appendix E for information regarding how the study will define and address patients who are lost to follow-up to help limit the amount and impact of missing data.

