If the reason for withdrawal from the study or discontinuation from IMP is an adverse event and/or adverse device effect, monitoring will be continued as applicable (eg, until the event has resolved or stabilized, until the patient is referred to the care of a healthcare professional, or until a determination of a cause unrelated to the IMP or study procedure is made). The specific event or test result (including repeated test results, as applicable) must be recorded both on the source documentation and in the CRF; both the adverse events page and/or adverse device effect page and the termination page of the CRF will be completed at that time. The investigator must inform the contract research organization (CRO) as soon as possible of each patient who is being considered for withdrawal due to adverse events. Additional reports must be provided when requested.

If a patient is withdrawn from the study or discontinues IMP for multiple reasons that include adverse events, the relevant page of the CRF should indicate that the withdrawal was related to an adverse event. An exception to this requirement will be the occurrence of an adverse event that in the opinion of the investigator is not severe enough to warrant discontinuation but that requires the use of a prohibited medication, thereby requiring discontinuation of the patient. In such a case, the reason for discontinuation would be "need to take a prohibited medication," not the adverse event.

In the case of patients lost to follow-up, attempts to contact the patient must be made and documented in the patient's medical records and transcribed to the CRF.

All assessments should be performed according to the protocol for the end of treatment visit or upon early termination if possible. Patients are required to return the FS eMDPI and Albuterol eMDPI (used and unused) upon withdrawal from the study.

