9.5.4. Planned Method of Analysis

9.5.4.1. Primary Analysis

To analyze the primary variable, the following estimand framework will be used:

- 1. Population: The patients met all of the inclusion criteria and none of the exclusion criteria. The mITT analysis set will be the primary analysis set for the primary endpoint.
- 2. Variable: The primary endpoint will be a binary response variable at Week 24. A patient will be defined as a responder if the patient achieves an ACT score of greater than or

CLN0035849 Version 2.0 Approved Page 71 of 98

- equal to 20 or an increase of greater than or equal to 3 ACT units from baseline to Week 24. Otherwise, the patient will be defined as a nonresponder.
- 3. Intercurrent events: Treatment discontinuation due to an adverse event, lack of efficacy, technology failure, disliking the DS, disliking IMP, or other reasons. For those who discontinue the treatment before Week 24, no further data will be collected.
- 4. Population-level summary: The primary endpoint will be analyzed using a logistic model, where binary variable responder rate (Yes/No) will be modeled through logit link function, with baseline ACT score and treatment as explanatory factors. For those who discontinue the treatment before Week 24 due to technology failure, disliking the DS, or disliking IMP, the patients will be defined as nonresponders; for those who discontinue early not due to these reasons, the response at the ET visit will be used. The mean and 95% credible intervals of the response rates and OR from the posterior distributions will be calculated and presented. An informative prior will be assumed for the model coefficient for treatment and non-informative priors will be assumed for all other model coefficients. The details for the data analysis will be specified in the Statistical Analysis Plan.

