6.2.2. Primary Analysis

To analyze the primary variable, the following estimand framework will be used:

1. Population: The patients met all of the inclusion criteria and none of the exclusion criteria. The mITT analysis set will be the primary analysis set for the primary endpoint.
2. Variable: The primary endpoint will be a binary response variable at Week 24. A patient will be defined as a responder if the patient achieves an ACT score of greater than or equal to 20 or an increase of greater than or equal to 3 ACT units from baseline to Week 24. Otherwise, the patient will be defined as a nonresponder.
3. Intercurrent events: Treatment discontinuation due to an adverse event, lack of efficacy, technology failure, disliking the DS, disliking IMP, or other reasons. For those who discontinue the treatment before Week 24, no further data will be collected.
4. Population-level summary: The primary endpoint will be analyzed using a logistic model, where binary variable responder rate (Yes/No) will be modeled through logit link function, with baseline ACT score and treatment as explanatory factors. For those who discontinue the treatment before Week 24 due to technology failure, disliking the digital platform, adverse event related to IMP, or disliking the IMP, the patients will be defined as nonresponders; for those who discontinue early not due to these reasons, the response

at the ET visit will be used. The mean and 95% credible intervals of the response rates and OR from the posterior distributions will be calculated and presented. An informative prior will be assumed for the model coefficient for treatment and non-informative priors will be assumed for all other model coefficients.

Logistic regression model allowing for different response rates at enrolling investigational centers will be used for testing the hypothesis $H_0: \beta_1 = 0, H_1: \beta_1 > 0$ in the following model:

$$\ln\left(\frac{p_{ij}}{1-p_{ij}}\right) = \beta_0 + \beta_1 x_i + \beta_2 \text{baseline ACT value} + \text{Center}_j$$

where x_i = treatment group i , p_{ij} = response proportion of treatment group i at Center j, Center_j = random center effect of center j.

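### The reason for stopping decides the primary outcome, but the CRF's adverse-event precedence can hide a listed failure reason, and the SAP's two failure lists conflict

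*Protocol*

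**What the plan says.** **How the reason is recorded.** Protocol 4.3 asks for a source narrative of the reason or reasons, and then: "The case report form (CRF) must document the primary reason for withdrawal from the study or discontinuation from IMP". Where a patient stops "IMP for multiple reasons that include adverse events, the relevant page of the CRF should indicate that the withdrawal was related to an adverse event". There is one exception: an event judged not severe enough to stop for, but "that requires the use of a prohibited medication, thereby requiring discontinuation of the patient". In that case the need for the prohibited drug is recorded as the reason in place of the event. The only prohibited drugs named (Protocol 4.3 and 5.6) are other SABA products, and 5.6 applies the ban to the DS group.

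**How the reason is used.** The plan contains three lists of reasons that make an early discontinuation a failure:

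- Protocol 9.5.4.1: discontinuation "due to technology failure, disliking the DS, or disliking IMP, the patients will be defined as nonresponders"; otherwise, "for those who discontinue early not due to these reasons, the response at the ET visit will be used".
- SAP 6.2.2: discontinuation "due to technology failure, disliking the digital platform, adverse event related to IMP, or disliking the IMP, the patients will be defined as nonresponders", with the same ET provision for everyone else. SAP 11 declares the addition of IMP-related adverse events as a change from the protocol.
- SAP 4.3: technology failure, dislike of the platform or of the IMP, disease worsening, and any adverse experience. A patient who stops early without an ET visit is also a failure.

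The SAP introduction gives the SAP precedence over the protocol. Nothing settles a conflict between two sections of the SAP.

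**The concern.** The adverse-event precedence in Protocol 4.3 is a sensible safety-reporting convention, but the primary endpoint depends on the same reason. If the endpoint is derived from the coded reason, a listed failure reason can disappear behind an adverse-event code. The protocol synopsis states the intent plainly: withdrawals for technology failure, or for disliking the technology or the IMP, count as nonresponders. Most of these reasons can arise only in the DS group, the trial is open-label, and the site assigns the reason.

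Neither document ranks multiple reasons for the endpoint or says which field drives it. The planned sensitivity analyses would not reveal a misclassification. SAP 6.2.3 analysis 1 uses the same reason categories to decide who has missing data and keeps the ET ACT for the rest; analysis 2 only drops the centre effect.

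**Working it through.** **Step 1. Score two cases under each list.**

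Case A is a DS patient whose reasons for leaving are technology failure and an adverse event unrelated to IMP, coded as adverse event. Case B is a DS patient with asthma worsening, not related to IMP and judged not severe enough to stop for, who needs another SABA and is coded as needing a prohibited medication.

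| List | A, by technology failure | A, by the CRF code | B, as asthma worsening | B, by the CRF code |
|---|---|---|---|---|
| Protocol 9.5.4.1 | nonresponder | ET ACT | ET ACT | ET ACT |
| SAP 6.2.2 and 11 | nonresponder | ET ACT | ET ACT | ET ACT |
| SAP 4.3 | failure | failure | failure | ET ACT |

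Case A changes score under SAP 6.2.2 but not under SAP 4.3. Case B changes score under SAP 4.3 but not under SAP 6.2.2; under 6.2.2 the prohibited-medication code matters only if the underlying event was related to IMP. The two routes therefore belong to different readings of the SAP, and their counts should not be added.

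**Step 2. Reproduce the plan's operating characteristic.** Inputs from SAP 2.4: 200 DS and 150 SoC patients; priors Beta(0.5, 0.5) for DS and Beta(9.52, 11.88) for SoC; success if P(OR>1) is at least 0.95. The method sums over all outcomes of Bin(200, p_DS) × Bin(150, p_SoC) with beta posteriors. At 58% v 45% the chance of success is 81.7%, matching the stated value of about 82%. At 45% v 45% it is 4.6%. This calculation is unadjusted; it omits baseline ACT and the centre effect.

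**Step 3. Effect of flips.** One DS patient moved from nonresponder to responder adds 1/200 = 0.5 points. With m flips, p_DS = 0.45 + m/200 and p_SoC = 0.45:

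| Flips m | Shift in DS rate (points) | Chance of success, no true effect |
|---|---|---|
| 0 | 0 | 4.6% |
| 1 | 0.5 | 5.6% |
| 2 | 1.0 | 6.9% |
| 3 | 1.5 | 8.3% |
| 4 | 2.0 | 9.9% |

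**Step 4. How many flips are plausible?** The documents do not say, so this is an assumed range. DS patients enrolled: 388 × 4/7 ≈ 222; early dropouts at 10%: about 22. Let f be the share of these whose listed reason is hidden by the code, and r the share of those who meet the ACT criterion at the ET visit. Then m = 22 × f × r.

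- f = 10%, r = 45%: m = 22 × 0.10 × 0.45 = 0.99, about one flip.
- f = 20%, r = 45%: m = 22 × 0.20 × 0.45 = 1.98, about two.
- f = 30%, r = 60%: m = 22 × 0.30 × 0.60 = 3.96, about four.

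Four flips thus need nearly a third of all DS dropouts to be hidden in this way, and most of those to respond at the ET visit.

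**The case against.** Much of the case against a stronger reading stands.

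- A reader might infer that any adverse event present at withdrawal triggers the recode. It does not: the event must itself be a reason for leaving. A patient who stops because the App fails and merely happens to have a cold has one reason, technology failure.
- A reader might infer that every mixed-reason withdrawal can become a prohibited-medication withdrawal. That code is a narrow exception, and nothing sends a technology or dislike case to it. Case B also does not breach the stated intent on technology failure and dislike; it conflicts only with the disease-worsening rule in SAP 4.3.
- A reader might infer a shift in one direction and one arm. An adverse event coded as IMP-related gives a nonresponder under SAP 6.2.2, and a patient without an ET visit is a failure under SAP 4.3. Disliking the IMP can also apply in SoC, because SoC medication is defined as IMP.
- A reader might infer that asthma worsening drops out of the safety tables. It could leave the table of events causing withdrawal, but it is still recorded and summarised among all and asthma-related adverse events (SAP 8.4).
- Neither document says that the analysis uses the CRF code alone. The CRF is not available here and may hold more than one reason.

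The last point weakens the claim that the code overrides the endpoint rule, but does not remove the gap. Protocol 4.3 asks for one primary reason, and its exception implies that the adverse event is otherwise the coded one. The SAP gives no other source and no ranking.

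**Conclusion.** The point holds in limited form. Under SAP 6.2.2 and 11, the coding rule can send a patient with a listed failure reason to the ET ACT, against the protocol's intent. If SAP 4.3 governs instead, that route closes, but an asthma worsening coded as needing a prohibited medication escapes the disease-worsening rule, and the SABA ban makes that route specific to the DS group. The conflict between SAP 4.3 and 6.2.2 leaves it open which of these applies.

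The size cannot be fixed from the documents. One to four flips would move the DS rate by 0.5 to 2.0 points and the false-success rate at 45% v 45% from 4.6% to between 5.6% and 9.9%. This rests on the unadjusted beta-binomial rule, 200 and 150 patients analysed, derivation from the coded reason, and an assumed number of flips. The bias is possible and probably small. The planned sample size and power are not in error on this account.

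**What to change.** Before database lock:

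1. Reconcile the failure lists in SAP 4.3 and 6.2.2 so that one list governs the primary endpoint.
2. Keep the adverse-event precedence of Protocol 4.3 for the safety tables only.
3. Capture all contributing reasons on the CRF termination page. The source narrative already requires them, so they can be abstracted for patients who have already left.
4. State in SAP 6.2.2 that a patient is a nonresponder if any contributing reason is on the list, whichever is coded as primary. Use the same classification in SAP 6.2.3 to decide whose values are set to missing.
5. State how prohibited-medication withdrawals are scored, consistently with the handling of the underlying event.

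The cost is one multi-select CRF field, or abstraction from source, and a few sentences in the SAP. No visits or patients are added. The DS response rate may come out slightly lower.

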4.4. Replacement of Patients

A patient who is enrolled but does not complete the treatment period will not be replaced.

4.5. Rescreening

A patient who is screened but not enrolled within 7 days of screening, because he/she did not satisfy inclusion/exclusion criteria or enrollment did not occur within the specified time, may be considered for rescreening once if, for example, there is a change in the patient's medical background or a modification of study inclusion and exclusion criteria.

Patients may have individual parameters retested at the discretion of both the investigator and the sponsor.

If the patient is rescreened, the informed consent form (ICF) will need to be resigned.

4.6. Screening Failure

Screening failures are defined as participants who consent to participate in the clinical study but are not subsequently enrolled in the study. Minimal information includes, but is not limited to, demography, screening failure details, eligibility criteria, and any serious adverse events.

5. TREATMENTS

5.1. Investigational Medicinal Products Used in the Study

The DSs consist of 4 devices each:

Test IMPs:

- FS eMDPI DS with 4 component devices:
 - Device 1: FS eMDPI
 - Device 2: Patient-facing smart device App (same for both IMPs)
 - Device 3: DHP (Cloud solution, same for both IMPs)
 - Device 4: Provider-facing dashboard (same for both IMPs)
- Albuterol eMDPI DS with 4 component devices:
 - Device 1: Albuterol eMDPI
 - Device 2: Patient-facing smart device App (same for both IMPs)
 - Device 3: DHP (Cloud solution, same for both IMPs)
 - Device 4: Provider-facing dashboard (same for both IMPs)

At Visit 1, patients in the DS group will be trained on the use of the eMDPI (including instructions on how to use both the eMDPIs and the App). Upon demonstrating competency, patients in the DS group will have their maintenance ICS with LABA switched to the FS eMDPI (at a dose of fluticasone comparable to their most recent current ICS dose) and their rescue treatment switched to the Albuterol eMDPI. All other asthma maintenance medications, except for ICS with LABA, may be continued. The iHCP can add another controller medication other than an ICS with LABA, including a biologic, to the DS patient's treatment, if needed. Patients in the SoC group will be reimbursed or given a voucher to use to purchase their existing maintenance ICS with LABA and rescue medications. Patients in the DS group will receive a new FS eMDPI device and 1 Albuterol eMDPI device at Visit 1 and 1 FS eMDPI device at Visit 2. Periodically after Visits 1 and 2, patients will be shipped a new FS eMDPI device, which they will need to pair with the App. The patient will immediately stop using the old device and switch to the new device. Extra Albuterol eMDPI devices may be shipped as needed, based on the clinical judgment of the investigator. Upon receipt, the patient will pair the new device with the App and will immediately stop using the old device and switch to the new device. To trigger DTP shipments, after Visit 1, the investigational center will receive periodic email reminders to access the IRT system to confirm the dose of test IMP to be shipped to the patient. Confirmation of the dose is required before the next shipment can be sent.

Patients will be instructed to return all inhalers to the investigational center at Visit 2 and at the end of treatment visit or Early Termination (ET) visit.

